13. OBLIGATIONS OF THE INVESTIGATOR AND THE SPONSOR

13.1. Compliance with Ethical and Regulatory Guidelines

The investigator is responsible for ensuring that the clinical study is performed in accordance with the International Council on Harmonisation (ICH) GCP guidance documents.

13.2. Institutional Review Board/Independent Ethics Committee

Prior to enrollment of patients into the study, as required by the Food and Drug Administration (FDA) and other regulatory authorities, the protocol and informed consent document will be reviewed and approved by an appropriate IRB/IEC. By signing the Statement of Investigator Form (FDA Form 1572), the investigator assures that approval of the study protocol will be obtained from the IRB/IEC and that all aspects of the IRB/IEC review will be conducted in accordance with current regulations. Amendments to the protocol will be subject to the same IRB/IEC review requirements as the original protocol. Only changes necessary to eliminate apparent immediate hazards to the patients may be initiated prior to IRB/IEC approval. In that event, the investigator must notify the IRB/IEC and PTC Therapeutics in writing within 5 working days after implementation. The investigator will also promptly notify the IRB/IEC of any serious, unexpected adverse events, or any other information that may affect the safe use of the drug during the course of the study, per local IRB/IEC requirements.

A letter documenting the IRB/IEC approval and a list of the names and titles of the IRB/IEC members must be received by PTC Therapeutics prior to the initiation of the study. All correspondence with the IRB/IEC should be retained in the investigator's study file.

The investigator or the sponsor shall submit a progress report, at least once yearly, to the IRB/IEC, as applicable, according to local regulations. A copy of any progress report submitted by the investigator must be provided to PTC Therapeutics. PTC Therapeutics will provide to the investigator a copy of any progress report submitted to the IRB/IEC. As soon as possible after completion or termination of the study, the investigator will submit a final report to the IRB/IEC, as applicable, and to PTC Therapeutics. This report should include the following:

Dates of initiation and completion of the study, a description of any changes in study procedures or amendments to the protocol, any deviations from the protocol, the number and type of patients evaluated, the number of patients who discontinued (and the reasons for discontinuation), the number of patients who completed the study, and the results of the study, including a description of any adverse events. PTC Therapeutics will assist the investigator in the preparation of this report, as needed.

If this study is performed under a grant from the US government, PTC Therapeutics will also submit the protocol and informed consent documents to the company's IRB of record (Western Institutional Review Board [WIRB], Olympia, WA). PTC Therapeutics or its designee will be responsible for all interactions with WIRB relating to the study, including submission of protocol documents, consent forms, and amendments; submission of adverse event reports and annual reports; receipt of approval notices; and exchange of other correspondence.

13.3. Informed Consent/Assent

By signing the Statement of Investigator (FDA Form 1572), the investigator assures that informed consent/assent will be obtained from each patient and/or parent/legal guardian prior to

study entry and that the informed consent/assent will be obtained in accordance with current regulations.

The investigator or sub-investigator will give each patient and/or parent/guardian full and adequate verbal and written information regarding the objectives and procedures of the study and the possible risks involved. An informed consent/assent document will be provided to each patient and/or parent/guardian in a language in which the patient or parent/guardian is fluent. This information must be provided to the patient or parent/guardian prior to undertaking any study-related procedure. Adequate time should be provided for the patient and/or parent/guardian to read the informed consent, to understand the risks and benefits of participating in the study, and to ask any questions that the patient and/or parent/guardian may have about the study. The patient and/or parent/guardian should be able to ask additional questions as and when needed during the conduct of the study. The patient's and/or parent/guardian signature on the informed consent form should be obtained at the investigator site in the presence of the investigator or a qualified representative (eg, sub-investigator). Where applicable, the patient will sign an age-appropriate assent form.

Each patient or parent/guardian will be given a copy of the signed consent/assent form. The original signed informed consent forms will be retained by the investigator with the study records.

The written patient information must not be changed without prior approval by PTC Therapeutics and the IRB/IEC.

13.4. Case Report Forms

An eCRF or paper CRF, as applicable, is required and must be completed for each enrolled patient, with all required study data accurately recorded such that the information matches the data contained in medical records (eg, physicians' notes, nurses' notes, clinic charts, and other study-specific source documents). The eCRFs exist within a Web-based EDC system managed by the data management contract research organization (CRO) for this study. After the investigator or the investigator's designees (eg, research coordinators) have been appropriately trained, they will be given access to the EDC system and will enter the data required by the protocol into the EDC system. Any change of data will be made via the EDC system, with all changes tracked by the system to provide an audit trail.

With an electronic signature, the investigator certifies that the data are complete and accurate prior to database lock. This electronic signature serves to attest that the information contained in the eCRFs is true. After database lock, the investigator site will retain read-only access to their respective eCRF data (as entered in the EDC system) for a period of up to 6 months following database lock. The investigator will have opportunity to review CD-ROM and/or paper copies of eCRF data against the read-only data (serving as a contemporaneous and independent copy of CRF). At all times, the principal investigator has final responsibility for the accuracy and authenticity of all clinical data entered onto the CRFs and/or reported to PTC Therapeutics from the investigator site.

13.5. Study Records

During the study, the investigator will maintain adequate records for the study, including the following:

- Medical records
- Source document records detailing the progress of the study for each patient
- Laboratory reports
- A CD-ROM or paper copies of the data that have been captured in the EDC for each patient
- Signed informed consent forms
- Delegation of Responsibility/Authority Log
- Ataluren drug accountability, reconciliation and disposition records
- Relevant equipment maintenance and calibration records
- Correspondence with the IRB/IEC
- Adverse event reports
- Information regarding patient discontinuation and completion of the study

Current regulations require PTC Therapeutics (or an authorized designee) to inspect all documents and records required to be maintained by the investigator, including but not limited to medical records (office, clinic, or hospital) for the patients enrolled in this study. These regulations also allow the same records to be inspected by authorized representatives of the FDA or other regulatory authorities.

13.6. Confidentiality

Research records will be collected and stored in a manner that protects the confidentiality of patient information. The names and identities of all research patients will be kept in strict confidence and will not appear on eCRFs, paper CRFs, or other records provided to or retained by PTC Therapeutics (or its authorized designee). The names and identities of the patients need not be divulged; however, the records must nevertheless be inspected. This will be accomplished by redacting the patient's name and replacing the name with the patient's study identification number on any record provided to or retained by PTC Therapeutics. The informed consent form must include appropriate statements explaining these requirements.

Attention is drawn to the regulations promulgated by the FDA under the Freedom of Information Act providing, in part, that information furnished to clinical investigators and the IRB/IEC will be kept confidential by the FDA only if maintained in confidence by the clinical investigator and the IRB/IEC. By signing this protocol, the investigator affirms to PTC Therapeutics that the investigator will maintain, in confidence, information furnished by PTC Therapeutics and will divulge such information to the IRB/IEC under an appropriate understanding of confidentiality with such board. In other countries where this clinical trial is conducted, the investigator and the sponsor will comply with the local data protection requirements, as applicable.

13.7. Retention of Records

To enable evaluations and/or audits from regulatory authorities or PTC Therapeutics, the investigator agrees to keep accurate and complete records, including the identity of all participating patients (sufficient information to link eCRFs and clinic records), all original signed informed consent forms, CD-ROM or paper copies of the data that have been captured in the

EDC for each patient (electronic equivalents of CRFs), and detailed records of study drug disposition. All records and documents pertaining to the study (including but not limited to those outlined in Section 13.5) will be maintained by the investigator until notification is received from PTC Therapeutics that the records no longer need to be retained.

The investigator must obtain written permission from PTC Therapeutics before disposing of any records. In order to avoid any possible errors, the investigator will contact PTC Therapeutics prior to the destruction of any study records. The investigator will promptly notify PTC Therapeutics in the event of accidental loss or destruction of any study records. If the investigator relocates, retires, or for any reason withdraws from the study, the study records may be transferred to an acceptable designee, such as another investigator or another institution. Precautions should be taken to ensure the integrity, security, and protection of these documents from damage or loss at all times during and after completion of the study.

13.8. Monitoring and Auditing

In accordance with 21 Code of Federal Regulations (CFR) Part 312.56 and/or relevant ICH guidelines, PTC Therapeutics or a designee will periodically inspect all eCRFs (see Section 13.4), study documents, research facilities, and clinical laboratory facilities associated with this study at mutually convenient times, before, during, and after completion of the study. As required by applicable regulations (Responsibilities of Sponsors and Investigators), the monitoring visits provide PTC Therapeutics with the opportunity to evaluate the progress of the study; verify the accuracy and completeness of data in the eCRFs; ensure that all protocol requirements, applicable FDA and other relevant regulations, and investigator's obligations are being fulfilled; and resolve any inconsistencies in the study records. This includes inspection of all documents and records required to be maintained by the investigator, including but not limited to medical records (office, clinic, or hospital) for the patients in this study. The names and identities of all research patients will be kept in strict confidence and will not appear on eCRFs or other records provided to or retained by PTC Therapeutics. The investigator/institution guarantees direct access to source documents by PTC Therapeutics and appropriate regulatory authorities.

The investigator site may also be subject to review by the IRB/IEC, to quality assurance audits performed by PTC Therapeutics or a designee, and/or to inspection by the FDA and/or other regulatory authorities. The Investigational New Drug (IND) regulations also require the investigator to allow authorized representatives of the FDA to inspect and make copies of the same records.

It is important that the investigator and relevant institutional personnel are available during the monitoring visits and possible audits or inspections and that sufficient time is devoted to the process.

13.9. Termination of the Study

PTC Therapeutics reserves the right to discontinue the study prior to inclusion of the intended number of patients. The investigator, after consultation with the PTC Therapeutics medical monitor, reserves the right to discontinue the study at the investigator site for safety reasons at any time.

After a decision to terminate the study, investigators must contact all patients who are continuing their participation in the study and must do so within a time-period set by PTC Therapeutics. As

directed by PTC Therapeutics, all study materials must be collected and all electronic data entry forms completed to the greatest extent possible.

13.10. Public Notification of Study Conduct

Consistent with Section 113 of the Food and Drug Modernization Act of 1997 (FDAMA) and with requirements of the International Committee of Medical Journal Editors (ICJME) as a condition of consideration for publication of study results, PTC Therapeutics will be responsible for ensuring that this protocol is listed at the ClinicalTrials.gov website. Information from ClinicalTrials.gov is provided to other publically available and/or electronically linked databases, including the WHO International Clinical Trials Registry Platform (ICTRP).

The protocol will also be listed in the EU Clinical Trials Register, the EU clinical trials database, as extracted from EudraCT. The information provided by PTC Therapeutics is a component of its application to a national medicines regulatory authority for authorization to conduct the study. The information from PTC Therapeutics is loaded into the EudraCT database by the national medicines regulatory authority.

PTC Therapeutics will ensure that information on the websites relating to study design and conduct is appropriately updated during the course of the study. In order to facilitate this process, investigators will need to supply PTC Therapeutics with appropriate contact information for investigator site personnel.

13.11. Dissemination of Results

The information developed during the conduct of this clinical study is considered confidential by PTC Therapeutics. This information may be disclosed as deemed necessary by PTC Therapeutics.

To allow for the use of the information derived from this clinical study and to ensure compliance with current regulations, the investigator is obliged to provide PTC Therapeutics with complete test results and all data developed in this study. The information obtained during this study may be made available by PTC Therapeutics to other physicians who are conducting similar studies and to the FDA or other regulatory authorities. Such information may be disclosed as deemed necessary by PTC Therapeutics.

PTC Therapeutics intends that the data from this study will be presented and published. The PTC Therapeutics staff under the direction of the PTC Therapeutics chief medical officer in collaboration with the investigator will be responsible for writing presentations and manuscripts for publication. Investigators will not be allowed to publish or present the data from this study without prior agreement with PTC Therapeutics.

13.12. Communication with Regulatory Authorities

PTC Therapeutics will assume responsibility for regulatory interactions with the FDA, the European Medicines Agency (EMA), and/or other regulatory authorities. In this regard, PTC Therapeutics will maintain an IND for ataluren in support of the study. In fulfilling this responsibility, PTC Therapeutics (or a designee) will collect, assemble, and communicate all required regulatory documents (eg, Form FDA 1572, investigator financial disclosure forms, protocol and protocol amendments, investigator brochures, informed consent documents, annual reports) as required by regulation. PTC Therapeutics (or a designee) will also assume responsibility for adverse event reporting to regulatory authorities as described in Section 9.10.

14. RATIONALE FOR STUDY DESIGN FEATURES

14.1. Patient Selection

14.1.1 Overview

Since this protocol describes an open-label extension study, enrollment is limited to the patients who successfully complete the double-blind, placebo-controlled Phase 3 study (PTC124-GD-021-CF). The eligibility criteria are designed to enable enrollment of patients who are sufficiently well (both in terms of CF and in terms of concomitant illness) to safely participate in study procedures and provide interpretable results. Consistent with GCP guidelines, patients and/or parent must provide informed consent/assent before initiation of any study procedures. To minimize missing data and premature discontinuations, patients must have the personal and family resources to comply with study procedures and restrictions. In addition, patients must not have serious concomitant conditions that would compromise safety, compliance, or evaluation.

14.1.2 Reproductive Considerations

Ataluren is not genotoxic, did not affect fertility in male and female rats, and was not teratogenic in rats and rabbits. In addition, lack of sexual maturity in many of the patients likely to be enrolled in this study limits reproductive risks. However, restriction on eligibility relating to willingness to avoid unprotected sexual intercourse in any patients known to be sexually active is included as a general precaution. Because it is unknown if ataluren is excreted in breast milk, lactating female patients who are breast-feeding are excluded from participation.

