4. PATIENT SELECTION CRITERIA

4.1. Overview

This clinical study can fulfill its objectives only if appropriate patients are enrolled. The following eligibility criteria are designed to select patients for whom study participation is considered appropriate. All relevant medical and non-medical conditions should be taken into consideration when deciding whether this protocol is suitable for a particular patient. Eligibility criteria may not be waived and conformance to the eligibility criteria is subject to review in the case of a Good Clinical Practice (GCP) or a regulatory authority audit. Any questions regarding a patient's eligibility should be discussed with the PTC Therapeutics medical monitor prior to enrollment.

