4.2. Inclusion Criteria

Patients must meet all of the following conditions to be eligible for enrollment into the study:

- 1. Completion of study treatment (placebo or active) in the previous Phase 3, double-blind study protocol (Protocol PTC124-GD-021-CF).
- 2. Evidence of signed and dated informed consent/assent document(s) indicating that the patient (and/or his parent/legal guardian) has been informed of all pertinent aspects of the trial. *Note: If the study candidate is considered a child under local regulation, a parent or legal guardian must provide written consent prior to initiation of study screening procedures and the study candidate may be required to provide written assent. The rules of the responsible Institutional Review Board/Independent Ethic Committee (IRB/IEC) regarding whether one or both parents must provide consent and the appropriate ages for obtaining consent and assent from the patient should be followed.*
- 3. In patients who are sexually active, willingness to abstain from sexual intercourse or employ a barrier or medical method of contraception during the study drug administration and 4-week follow-up period.
- 4. Willingness and ability to comply with scheduled visits, ataluren administration plan, study procedures, laboratory tests, and study restrictions.

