4.3. Exclusion Criteria

Prior to treatment with study drug, it will be confirmed that the patient meets none of the following conditions:

- Known hypersensitivity to any of the ingredients or excipients of the study drug (Litesse® UltraTM [refined polydextrose], polyethylene glycol 3350, Lutrol® micro F127 [poloxamer 407], mannitol 25C, crospovidone XL10, hydroxyethyl cellulose, vanilla, Cab-O-Sil® M5P [colloidal silica], magnesium stearate).
- 2. Ongoing participation in any other therapeutic clinical trial.
- 3. Prior or ongoing medical condition (eg, concomitant illness, psychiatric condition, behavioral disorder, alcoholism, drug abuse), medical history, physical findings, ECG findings, or laboratory abnormality that, in the investigator's opinion, could adversely affect the safety of the patient, makes it unlikely that the course of treatment or follow-up would be completed, or could impair the assessment of study results.

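### Section 14.1.2 says breast-feeding patients are excluded, but no criterion in Sections 4.2–4.3 excludes them

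*Protocol*

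**What the plan says.** Section 14 of the protocol gives the reasons for the design. Its paragraph on reproduction (14.1.2) says that "lactating female patients who are breast-feeding are excluded from participation", and gives as the reason that passage of ataluren into breast milk has not been established. The sentence is unqualified.

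Eligibility itself is set in Section 4. Section 4.1 says: "Eligibility criteria may not be waived and conformance to the eligibility criteria is subject to review". Section 4.2 has four inclusion criteria: completion of parent-study treatment, consent or assent, contraception, and willingness and ability to comply. Section 4.3 requires that before dosing "it will be confirmed that the patient meets none of the following conditions", and lists three: hypersensitivity to an ingredient, participation in another therapeutic trial, and a condition or finding that the investigator judges disqualifying.

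Neither list mentions lactation or breast-feeding. Both read as complete, with no sign of redaction or lost text.

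**The concern.** Section 14 explains criteria; Section 4 is where they are set and checked. Here the explanation describes an exclusion that the operative list lacks. Because the Section 4 criteria are the non-waivable, auditable standard, a site can comply with them fully and still enrol a patient whom Section 14.1.2 says is not in the study. An audit against Section 4 would not pick this up.

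What is at stake is the possible exposure of a breast-fed infant, during treatment planned for up to 96 weeks, to a drug whose excretion in milk is unknown. This is a question of safety and internal consistency. It does not bear on error rates, sample size or estimation.

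**Working it through.** No formula applies. The check sets the texts side by side.

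**Step 1. Could an existing Section 4 criterion do the job?**

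- *Inclusion 3* is the only reproductive criterion. It asks sexually active patients to abstain or "employ a barrier or medical method of contraception". That concerns conception, not lactation.
- *Exclusion 3* is the nearest general clause. It depends on the investigator's opinion and covers a condition, history or finding that "could adversely affect the safety of the patient", makes completion unlikely, or could impair assessment of the results. The reason given in 14.1.2 is drug in milk, which concerns the infant and is none of these three. A discretionary clause also cannot carry out an unconditional exclusion.
- The remaining five criteria concern other matters.

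Result: 0 of 4 + 3 = 7 criteria name breast-feeding or clearly imply it.

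**Step 2. Is the rule supplied elsewhere?** Section 8.2.9 provides for serum β-HCG at every visit in females. That tests for pregnancy and does not identify a breast-feeding patient. The schedule of events (Table 3) has no lactation check, and the SAP is silent. The exclusion appears only in 14.1.2.

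**Step 3. Does the rationale routinely state restrictions that Section 4 lacks?** The entry restrictions in 14.1.1–14.1.3 map to Section 4 as follows.

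| Rationale | Restriction | Criterion in Section 4 |
|---|---|---|
| 14.1.1 | "enrollment is limited to the patients who successfully complete" the parent study | Inclusion 1 |
| 14.1.1 | Patient or parent "must provide informed consent/assent before initiation of any study procedures" | Inclusion 2 |
| 14.1.1 | "patients must have the personal and family resources to comply with study procedures and restrictions" | Inclusion 4 |
| 14.1.1 | No serious concomitant condition | Exclusion 3 |
| 14.1.2 | Avoidance of unprotected intercourse | Inclusion 3 |
| 14.1.2 | Not breast-feeding | none |
| 14.1.3 | Excipient allergy reviewed | Exclusion 1 |
| 14.1.3 | No concurrent therapeutic trial | Exclusion 2 |

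That is 4 + 2 + 2 = 8 restrictions, of which 7 match the 7 criteria one to one and 1 does not.

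The count involves some judgement, so I varied it. If the excipient review is not counted as a restriction, 6 of 7 match. If the general remark in 14.1.1 about being well enough to take part is counted separately and matched to Exclusion 3, 8 of 9 match. Breast-feeding is the single unmatched item each time. Within the patient-selection rationale, this looks like an accidental omission.

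**The case against.** The strongest reply is that Section 4 is not the only place where this protocol restricts entry. Section 7.1.4 bars patients who need certain CYP2C8 or CYP2C9 substrates, and Section 7.1.2 requires a washout from inhaled tobramycin when the gap between studies exceeds one month. Neither is in Section 4. Counting them with the eight above, 3 of 10 restrictions have no Section 4 counterpart. This stands as far as it goes: the one-to-one match holds only within 14.1.1–14.1.3. But the two Section 7 rules sit in operative medication instructions that sites must follow, whereas the breast-feeding rule appears only in explanatory text.

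Second, Section 4.1 also asks sites to weigh all relevant conditions and to take eligibility questions to the medical monitor, and Inclusion 4 requires compliance with study restrictions. Section 14.1.2 belongs to the same approved protocol, so a careful site could find the rule. This lowers the chance of an error but does not replace a criterion.

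Third, the parent study may have screened for breast-feeding, and patients should ideally transfer on the same day. The parent study's criteria are not in these documents, so this cannot be confirmed. Its treatment lasts 48 weeks and a gap before entry is allowed for, so a patient's status could change after any earlier screening.

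Fourth, a line in Section 4.3 acts only at entry and would not address breast-feeding that begins during treatment. That is correct, and it limits what the fix achieves.

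**Conclusion.** The inconsistency is real and the plan is wrong as written: one exclusion is stated in the rationale and none of the seven binding criteria implements it. The conclusion rests on the text alone and assumes only that sites and auditors work from Section 4, as Section 4.1 indicates.

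The practical size is small. Section 5.1 expects about 200 entrants, all parent-study completers, and 14.1.2 notes that many are likely to be sexually immature. How many could be breast-feeding cannot be derived from the documents and may be none. The infant risk is precautionary, since 14.1.2 says only that excretion in milk is unknown. Endpoints, populations and analyses are unaffected. SAP Section 2.1 records premature termination on 2 March 2017, so the point concerns the plan as written and would not change who was already enrolled. It should be corrected, as a minor safety-consistency error.

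**What to change.** Add one numbered exclusion to Section 4.3: *Female patients who are breast-feeding.* If the sponsor did not intend the exclusion, correct Section 14.1.2 instead; the two texts cannot both stand.

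Optionally, add a cross-reference in Section 4.3 to the drug-based entry rules in Sections 7.1.2 and 7.1.4, so that a site working from Section 4 sees every restriction.

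The cost is one line of text, with no new procedure and no change to the analysis. Under Section 13.2 it is a protocol amendment subject to IRB/IEC review, so it is best combined with another amendment.
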